Acceptability: Acceptability of ONS products will be explored with semi-structured interviews. The semi-structured interviews will consist of several key open-ended questions that will help define the areas explored but allow the interviewer or interviewee to expand and diverge with the aim of pursuing or developing an idea with more depth. The interviews will seek to explore the views of hospitalised older adults and healthcare professionals working on geriatric medical wards, exploring the acceptability of the ONS products. The interviews will be audio-recorded for data collection purposes. Interviews with staff will take place one-to-one with the research assistant either in a private office space within UHS in-person, or remotely via telephone, or Microsoft Teams (depending on participant preference). Patients will be interviewed following completion of 4 days of ONS intervention at bedside, or in a private room at UHS, depending on personal preference.

Data Analysis

Quantitative data analysis

Data collected will be double entered into a secured database for analysis. Statistical analysis will be conducted using the statistical software SPSS. Descriptive statistics -median (IQR); mean (SD); number (%) – will be used to analyse ONS ingested (%), intake of energy (kcal/day), intake of protein (g/day), and palatability Likert scores. Palatability Likert scores will be categorised into positive, neutral and negative scores and presented in bar charts to illustrate comparisons of each ONS product [47]. Compliance rates will be split into comparable groups with low, medium and high compliance categorised as $\leq 30\%$, 31-79%, and $\geq 80\%$, respectively, and presented in bar charts. Normality tests, including skewness and kurtosis, will be conducted to determine suitable statistical analyses for measures (i.e., non-parametric vs. parametric tests). Primary outcome measures will be compared between groups (treatment vs. control) using a repeated measures t-test, or Wilcoxon test, depending upon normality. Total daily energy intake (kcal) will be compared between ONS groups and to control (i.e., before testing) with a repeated measures ANOVA with Bonferroni correction to assess the impact of ONS on normal meal intake.

Qualitative data analysis

Interviews will be transcribed verbatim and analysed using reflexive thematic analysis (TA) [48]. TA is a method for identifying, analysing and reporting patterns or themes within data and is widely used in qualitative research. There are six phases in the process of conducting TA: Phase 1 – familiarising with the data, Phase 2 – generating initial codes, Phase 3 – searching for themes, Phase 4 – reviewing themes, Phase 5 – defining and naming themes, and Phase 6 – producing the report. Analysis of qualitative data will be conducted using either Microsoft Word, or with the help of NVIVO, depending on the amount of data collected. Transcribed text will be read and coded separately and then together by two researchers. The codes will be analysed to generate concepts and ideas to determine the acceptability of the intervention, and to identify facilitators and barriers to the implementation process. The codes act as tags or labels to help catalogue key concepts embedded within the raw data. From the codes, themes will be developed to reflect the views and experiences of the patients and healthcare professionals regarding the intake and use of ONS products in hospital.

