	
smell, leading to alterations in food or fluid consumption. Supplemental preference may be affected by a multitude of factors such as taste, colour, smell, after taste and texture. Typically, hospital patients are offered liquid based ONS (sip feeds). However, previous research has pinpointed that 56% of older adults on geriatric wards did not like sip feeds. Hence, exploration of compliance to different ONS formats is an important research direction to maximise malnourished older adult's nutritional intake.
 
Malnourished hospitalised older adults should be offered an improved range and provision of ONS to suit patient preferences and maximise intake. For instance, an attractive alternative strategy is the use of energy and protein-dense meals (via fortification) or snacks (supplementation), including fortified bread, protein-enriched main meals and between meal snacks, such as biscuits, yoghurt and ice cream. Yet this is an understudied area, with limited data investigating compliance to alternative ONS products compared to ready-made drinks in hospital, such as powdered ONS and snacks, or their clinical effectiveness. Therefore, the current study aimed to investigate the compliance and palatability of novel fortified porridge compared to traditional sip-feeds in malnourished hospitalised older adults.

Research Question/Aim(s)	
 1. What are the compliance rates (% intake) of fortified porridge compared to standard liquid based ONS in malnourished hospitalised older adults? 2. What are the palatability ratings (e.g., taste) of fortified porridge compared to standard liquid based ONS in malnourished hospitalised older adults? 3. What is the acceptability of fortified porridge compared to standard liquid based ONS in malnourished hospitalised older adults, including facilitators and barriers to their use on medical wards?

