5.2.1 Size of sample

A sample size of 50 was chosen based upon guidance from previous literature investigating compliance and palatability of ONS [22, 29]. In a systematic review of 49 studies assessing ONS compliance, studies included 1-4 groups (median 2) with a median of 30 (interquartile range 23-41) participants in each group [22]. In the current study a repeated measures two tailed t-test will be applied to compare compliance and palatability between 2 conditions (treatment vs. control).

To explore acceptability, 10-15 interviews will be conducted among patients (N= 7-9) and health care professionals (N= 3-6) to share their thoughts on using the ONS products and to capture their views regarding implementation of ONS products on the wards.

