5.2.2 Sampling technique

Older adults admitted to acute medical and orthogeriatric wards, who meet the eligibility criteria, will be recruited to the study. Purposive sampling will be used to recruit participants for interview, including a representative age range, ethnicity, and inclusion of a range of staff roles, including nurses (N= 2), health care assistants (N= 1), meal-time co-ordinators (N= 1), and doctors (N= 2).

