6.2 Research Ethics Committee (REC) and other Regulatory review & reports

This study will require ethical approval from the Health Research Authority (HRA). We will submit this study for review to the HRA NHS Research Ethics Committee through the Integrated Research Application System.

- Substantial amendments that require review by NHS REC will not be implemented until that review is in place and other mechanisms are in place to implement at site.
- All correspondence with the REC will be retained.
- It is the Chief Investigator's responsibility to produce the annual reports as required.
- The Chief Investigator will notify the REC of the end of the study.
- An annual progress report (APR) will be submitted to the REC within 30 days of the anniversary date on which the favourable opinion was given, and annually until the study is declared ended.
- If the study is ended prematurely, the Chief Investigator will notify the REC, including the reasons for the premature termination.
- Within one year after the end of the study, the Chief Investigator will submit a final report with the results, including any publications/abstracts, to the REC.

Discontinuation/Withdrawal of Participants from Study:

Each participant has the right to withdraw from the study at any time and request that any data collected be deleted. It will not be possible for the participant to withdraw their data once the analysis has started because the data collected will already be pseudonymised and have been used.

Participants can withdraw from the study without giving a reason by contacting the research team.

Withdrawal criteria:

- On the request of the research participant

The RELISH Study

- On the advice of the participant's clinical care team, such as in the event that the oral nutritional supplement becomes unsuitable for them

Regulatory Review & Compliance

Before any site can enrol participants into the study, the Chief Investigator/Principal Investigator will ensure that appropriate approvals from participating organisations are in place. Specific arrangements on how to gain approval from participating organisations are in place and comply with the relevant guidance.

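### Patient interviews are timed only for those who finish all 4 days, with no interview described for early stoppers, so barriers that make patients stop a product may be under-represented

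*Combined protocol and SAP*

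**What the plan says.** - **Question.** Item 3 of the research questions in the synopsis asks about the acceptability of both products, "including facilitators and barriers to their use on medical wards". Section 2.2 says the findings will help decide whether the porridge suits the hospital and a wider regional roll-out.
- **Timing.** Section 3, under the acceptability outcome, states: "Patients will be interviewed following completion of 4 days of ONS intervention", with the bedside or a private room as the place. Each product is given for 2 days, so 4 days means both crossover periods. No other time is given for patients.
- **Who is chosen.** Section 5.2.2 states: "Purposive sampling will be used to recruit participants for interview, including a representative age range, ethnicity, and inclusion of a range of staff roles". Compliance, dislike and early stopping are not named.
- **How many.** Section 5.2.1 plans 7–9 patient and 3–6 staff interviews, 10–15 in total. The synopsis gives the upper figures, 9 and 6.
- **Stopping.** Section 6.2 allows withdrawal on the care team's advice, "such as in the event that the oral nutritional supplement becomes unsuitable for them". It also says: "Participants can withdraw from the study without giving a reason by contacting the research team". It describes no exit interview and no recording of reasons.
- **Low intake.** Section 3 treats this as an outcome: "Compliance rates will be split into comparable groups with low, medium and high compliance", with the low band at 30% or less. Low intake is not a listed withdrawal criterion.

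**The concern.** A patient who stops a product because of its taste, its texture or feeling unwell has met a barrier strong enough to end use. If interviews take place only once both products have been finished, the sample is selected on having tolerated them, and the reasons for refusal may not be heard first-hand.

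The plan's own background makes strong dislike plausible. Section 1 reports that 56% of older adults on geriatric wards did not like sip feeds. In the survey of 25 patients in section 6.4, 32% rated porridge on the dislike side of the scale, and in the pilot 3 of 9 ate less than half the portion. None of these is a stopping rate. They show only that negative reactions should be expected and are worth sampling.

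At stake is the completeness of the answer to one stated research question that feeds a decision about wider use.

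**Working it through.** The plan states no figure on this point, so there is nothing to reproduce beyond the interview counts. These agree: 7 + 3 = 10, 9 + 6 = 15, and the staff roles in section 5.2.2 add to 2 + 1 + 1 + 2 = 6.

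**Who can reach an interview under the text as written**

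1. A patient who completes 4 days with good intake: yes, at the stated time.
2. A patient who completes 4 days but leaves most of one product: yes. Section 6.2 does not list low intake as a reason to withdraw, and section 3 has a band for it. Nothing in section 5.2.2 directs the team to seek such a patient.
3. A patient who stops before day 4: no interview time applies. No text forbids an interview, but none provides for one.

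Group 3 is therefore the gap in provision. Group 2 is only a gap in targeting.

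**Illustration of scale**

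Suppose early stoppers were eligible and interviewees were chosen without regard to stopping. With early-stopping rate p and n patient interviews, the chance of including at least one early stopper is 1 − (1 − p)^n. The values n = 7 and n = 9 come from section 5.2.1. The rate p is an assumption, because the documents give none. Expected stoppers are 50 × p, using the planned sample of 50.

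| Assumed p | Expected stoppers of 50 | n = 7 | n = 9 |
|---|---|---|---|
| 5% | 2.5 | 1 − 0.95^7 = 30% | 1 − 0.95^9 = 37% |
| 10% | 5 | 1 − 0.90^7 = 52% | 1 − 0.90^9 = 61% |
| 20% | 10 | 1 − 0.80^7 = 79% | 1 − 0.80^9 = 87% |
| 30% | 15 | 1 − 0.70^7 = 92% | 1 − 0.70^9 = 96% |

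Drawing without replacement from exactly 50 patients changes little: at 10% the figures become 55% and 65%, and at 20% they become 81% and 89%. If completion is applied as a condition, the chance is 0 at every p.

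Opening eligibility alone would often be enough if stopping were common. At 5–10% it would include an early stopper only 30–61% of the time, which is why the sampling criteria matter as well as the timing. The formula treats selection as random, whereas the plan's selection is purposive, so the table shows scale and does not predict what would happen.

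**The case against.** A reader might infer that early stoppers can never be interviewed, or that patients who disliked a product are excluded by rule. The documents support neither reading. The sentence in section 3 sets a time and place, and no section bars a withdrawn patient. The criteria in section 5.2.2 are introduced as examples and need not be exhaustive. The interview row in Appendix 2, which covers patients and staff together, also allows telephone or online contact. Patients who dislike a product but stay 4 days are eligible, and the patient interview guide asks them about bad points of each product, whether both daily portions were managed, and boredom.

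Other sources also bear on barriers. The staff guide asks what patients struggle with and what the disadvantages of the porridge are. Palatability is rated when each product is first introduced, on days 1 and 3, on a form with a comments field. The timing has a reason too: the question is comparative, and a patient who stops in the first period has tried one product only.

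Much of this stands, and it limits the point to a gap in provision and targeting. It does not close the gap. Staff accounts are second-hand. Ratings at first exposure cannot capture later fatigue or intolerance. The telephone and online option concerns where an interview happens and does not say who is eligible.

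**Conclusion.** The concern holds in a limited form. Followed as written, the plan would draw its patient interviews from completers, and barriers that lead patients to stop a product may be under-represented in the answer to research question 3. Low consumers who complete are eligible but not sought.

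The size of the effect is unknown. No early-stopping rate is given, and any overall non-completion rate would mix product-related stopping with discharge and illness. A reader might also conclude that barriers will certainly be under-reported and that both products will look better than they are. That direction is plausible, but nothing in the documents establishes it.

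The point concerns one qualitative secondary outcome and leaves compliance and palatability, the primary outcomes, untouched. It is worth acting on because a small change gives a less selective sample.

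**What to change.** - **Section 3, acceptability outcome:** state that patients are interviewed after completing, or on stopping, the supplements, if they agree, and that the interview covers whichever products they tried.
- **Section 5.2.2:** add compliance level, using the plan's existing low, medium and high bands, and early stopping to the purposive criteria. Keep the existing 7–9 patient interviews and set no fixed quota: at an assumed 5% rate only about 2.5 of 50 patients would stop early, before any refusals.

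**Cost.** No extra interviews are needed. Fewer completers would be interviewed, some interviews would cover one product only, and some early stoppers would decline. Because section 6.2 allows a patient to leave the study without giving a reason, the interview must remain optional. The wording change may need notifying as an amendment under section 6.2.

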2.2 Outcome

Exploration of the compliance, palatability, and acceptability of the ONS product will help to determine whether the product is appropriate for further evaluation in future research, to determine sample sizes for a controlled trial to investigate clinical outcomes of ONS and to assess whether the ideas and findings can be shaped to be relevant and sustainable. The study will also help to determine suitability of the product for use in UHS and for a larger roll out of the product across Wessex.

Through collaborations between University of Southampton, University Hospital Southampton and Adams Vital Nutrition Ltd. the anticipated impacts include:

- Explore the usability of additional ONS products to facilitate management of malnutrition in patient's at UHS.
- Lay a foundation for future randomised clinical trials.
- Dissemination of our research findings through scientific and lay platforms to encourage implementation in other settings.
- Improved nutrition support for older adults with malnutrition with potential benefit in health outcomes.

3 STUDY DESIGN and METHODS of DATA COLLECTION AND DATA ANALYSIS

Study Design

A mixed methods randomised controlled crossover design will be conducted to determine compliance and palatability of fortified porridge in malnourished hospitalised older adults. A crossover design was chosen to account for heterogeneity in an older patient population (e.g., differences in disease states and oral sensory perceptions), in which participants will act as their own controls to better compare palatability of products. This study will be conducted at University Hospital Southampton (UHS) NHS Foundation Trust on geriatric acute medical wards comparing intake and palatability of 'build and restore' fortified porridge (treatment) and standard liquid based ONS (control) in a repeated measures crossover design. The acceptability of products will be assessed through qualitative interviews to explore patients and healthcare professionals' experiences and views of using the different nutritional supplements.

Intervention

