Participants will be prescribed ONS twice per day for 4 days, in addition to normal meals, in a crossover design. Two ONS products (Table 1) will be tested for palatability and compliance including a new fortified porridge (treatment), and standard liquid-based ONS (control). Each ONS product will be tested over 2 days in a randomised crossover sequence (Figure 1). The products will be offered twice per day, in-between breakfast and lunch, and after dinner to reduce the detrimental long period of calorie absence experienced overnight [33]. The fortified porridge (treatment) is powdered and mixed with 100 ml boiling water in a carton with a choice of 4 flavours including golden syrup, apple and cinnamon, strawberries and cream, and bananas and custard. The liquid-based ONS (control) are ready-to-drink milkshakes. Participants will be offered the ONS in a screw-topped plastic bottle, and a choice from a variety of flavours (e.g., vanilla, strawberry, chocolate, banana, mocha, neutral, berries). ONS products will be prepared and distributed to participants by health care professionals working on the wards.

Table 1. ONS Product Information (see appendices for full product specification)

Group	Treatment	Control
Name	Vital Daily High Protein Oats (Adams Vital Nutrition Ltd.)	Anonymous readymade drink supplement
Description	Fortified 'build and restore' porridge ONS	Standard liquid-based ONS
Weight (g)	157	125
Energy (kcal)	230	306
Protein (g)	15	18.3

Data Collection

Participant Characteristics

Participant characteristics including age, domicile status, marital status, care provision, usual residence, frailty (PRISMA-7), sarcopenia (SARC-F), and appetite (SNAQ) will be assessed at baseline. Moreover, participants C-reactive protein [34] and National Early Warning Score [35] will be

recorded as markers of acute illness (recorded as part of standard care), a potential mediator of older adults' appetite [36].

Appetite will be measured using the Simplified Nutritional Appetite Questionnaire (SNAQ) [37], which has been validated to predict weight loss in community dwelling older adults and used to predict poor health outcomes in hospitalised older people [37-39]. SNAQ is a four-item tool comprising items 1, 2, 4 and 6 of the CNAQ, assessing appetite, satiety, taste of food and number of meals per day respectively. SNAQ has a maximum score of 20, with a score of ≤ 14 indicating poor appetite.

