The Strength, Assistance with walking, Rising from a chair, Climbing stairs, and Falls (SARC-F) questionnaire will be used as a measure to assess for sarcopenia [40]. It comprises five components: strength, assistance in walking, rise from a chair, climbing stairs and falls. The scores range from 0 to 10, with a score of equal to or greater than four being predictive of sarcopenia and poor outcome.

Program of Research to Integrate Services for the Maintenance of Autonomy (PRISMA-7) screening tool will be used to characterise participants' frailty status [41]. The questionnaire contains seven items with a positive score of three or more indicating frailty. The PRISMA-7 tool has been shown to have high accuracy in identifying frail older adults in the community setting [42].

Primary Outcome Measures

Primary outcome measures will include compliance to ONS and palatability.

Compliance: Compliance to ONS will be assessed by the study team via careful documentation of ONS leftovers at 2 timepoints, including after lunch (for ONS given in the morning) and early morning the following day (for ONS given after dinner), to ensure enough time for consumption. Leftovers will be weighed (g) using weighing scales (Seca Model 875 digital weighing scale) and documented by the research team. Compliance will be calculated as the percentage of the mean ONS consumed per day. Moreover, the mean intake of ONS energy (kcal/day) and protein (g/day) consumed per day will be calculated and an estimation of the percentage ingested.

Palatability: Palatability ratings, including appearance, smell, taste, sweetness, texture, thickness, aftertaste, mouth feel, and overall likability will be assessed with a 7-point hedonic Likert scale (7 = definitely like, 6 = moderately like, 5 = mildly like, 4 = neither like nor dislike, 3 = mildly dislike, 2 = moderately dislike, 1 = definitely dislike). Hedonic scales have been used to assess palatability of ONS supplements across population groups [24, 32, 43] and have good reliability [44]. Palatability ratings will be completed by participants on initial introduction of each ONS at a standardised time of day (i.e., morning ONS on day 1 and 3) (Figure 2).

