5.4 Randomisation Procedure

Once participants have completed informed consent each participant will be randomised in a crossover procedure to groups using a computer-generated randomization tool, 'Research Randomizer' [52], to minimise sequence effects and bias (Figure 2). Patients will be allocated to one of two sequences at random in a 1:1 allocation to eliminate bias associated with group assignment while creating similar sized groups.

Figure 2. Randomisation procedure

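### The primary paired t-test or Wilcoxon test ignores period in a two-sequence crossover, so a shift between periods inflates the reported error and, if the analysed sequences are unequal, moves the estimate

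*Combined protocol and SAP*

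**What the plan says.** The design is a two-product, two-period crossover. Section 3 (Intervention) states: "Each ONS product will be tested over 2 days in a randomised crossover sequence". Section 5.4 allocates patients to "one of two sequences at random in a 1:1 allocation to eliminate bias associated with group assignment while creating similar sized groups", and gives limiting order effects as a purpose of randomising. Compliance is therefore compared between days 1-2 and days 3-4. Section 3 (Primary Outcome Measures) has palatability rated at the morning product on days 1 and 3.

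The analysis is in Section 3 (Quantitative data analysis): "Primary outcome measures will be compared between groups (treatment vs. control) using a repeated measures t-test, or Wilcoxon test, depending upon normality". Section 5.2.1 repeats the parametric version: "a repeated measures two tailed t-test will be applied to compare compliance and palatability between 2 conditions". Nowhere in the text is period or sequence used in an analysis, and no summary by sequence is planned.

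Section 3 (Study Design) gives the reason for a crossover: "participants will act as their own controls to better compare palatability of products".

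**The concern.** Order is controlled when patients are allocated, but the analysis does not use that allocation. A patient's porridge-minus-liquid difference contains the product effect and also whatever changed between the first and second period. The change enters with opposite signs in the two sequences. A test on the pooled differences treats the gap between sequences as patient-to-patient noise.

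A crossover was chosen for its within-patient precision. A material period shift would make the reported interval wider than it should be. If the analysed sequences also differ in size, part of the shift would be reported as a product difference in that sample. Section 2.2 says the study will inform sample sizes for a later controlled trial, and an SD of differences that includes period variation would carry into that calculation.

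The documents give grounds for caution on both ingredients, and no figures. C-reactive protein and the early warning score are "recorded as markers of acute illness (recorded as part of standard care), a potential mediator of older adults' appetite". Section 6.2 allows withdrawal "On the advice of the participant's clinical care team, such as in the event that the oral nutritional supplement becomes unsuitable for them", which could unbalance the sequences that reach analysis.

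**Working it through.** **Inputs from the documents.** Two sequences, 1:1 (Section 5.4); two 2-day periods (Section 3, Intervention); n=50 and a two-sided paired t-test (Section 5.2.1). The plan gives no power calculation, so there is no figure of its own to reproduce.

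**Assumed.** SD of within-patient differences 30 percentage points (20 and 40 also tried), true difference 12 points, two-sided 5% level, shift p (period 2 minus period 1) of 0, 5, 10 or 15 points.

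**Model.** Let τ be the product difference, porridge minus liquid.

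- Porridge first: differences centre on τ − p.
- Liquid first: differences centre on τ + p.
- The paired mean estimates τ + p(n_liquid-first − n_porridge-first)/N.
- Expected reported variance of the paired mean: [SD² + 4p²·n1·n2/(N(N−1))]/N.
- The period-adjusted estimate is the average of the two sequence means. It is free of p and has variance (SD²/4)(1/n1 + 1/n2).

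**Equal sequences, 25/25.** The paired and adjusted estimates are the same number. The true sampling SD is 30/√50 = 4.24 at every shift. Only the reported SE changes. At p = 10 the expected reported variance is (900 + 4×100×625/2450)/50 = 20.04, root 4.48, against 18.00, root 4.24, without a shift. Simulation (40,000 replicates) gives the mean reported SE, which is slightly below these roots:

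| Shift | Reported SE, paired | Reported SE, adjusted | Type I error, paired | Power, paired | Power, adjusted |
|---|---|---|---|---|---|
| 0 | 4.22 | 4.22 | 5.0% | 79% | 79% |
| 5 | 4.28 | 4.22 | 4.6% | 78% | 79% |
| 10 | 4.45 | 4.22 | 3.9% | 76% | 79% |
| 15 | 4.73 | 4.22 | 2.9% | 72% | 79% |

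A 10-point shift inflates the reported SE by 12%, 6% or 3% if the SD is 20, 30 or 40.

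**Unequal sequences, 30/20, conditional on that split.** The estimate moves by p×10/50 = 0.2p, that is 1, 2 and 3 points at shifts of 5, 10 and 15. Paired type I error is about 5%, 6% and 7%, against 5% adjusted. Paired power is 71%, 60% and 46% when the movement opposes the true effect and 85%, 88% and 90% when it favours it, against 77-78% adjusted.

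Adjustment does not reduce sampling variance here. The true SD is 4.24 paired and 15×√(1/30 + 1/20) = 4.33 adjusted. What it does is remove the bias and give a valid SE. On mean squared error it is better once 0.04p² exceeds 18.75 − 18.00 = 0.75, that is above a shift of about 4.3 points.

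**Milder imbalance, 28/22.** The estimate moves by 0.12p, and type I error stays at or below about 5%.

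**Averaged over simple randomisation** (assumed; the text names no scheme). Paired type I error is 4.9-5.1%. Paired power is 79%, 78%, 75% and 70%, against 78% adjusted. A split of 30/20 or worse has probability 20%.

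**Likert items** (assumed between-patient SD 1.0, within-patient SD 1.2, product difference 0.75, shifts 0, 0.5 and 0.8). The rank tests follow the same pattern. At 25/25, Wilcoxon power is 82%, 80% and 76%, against 81% throughout for Mann-Whitney on period differences. At 30/20, conditional Wilcoxon type I error is 4.5%, 5.6% and 6.7%, against 4.2%, 5.2% and 4.9%.

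**The case against.** The strongest reply is that randomising order already protects the comparison. In large part it does. With equal sequences the estimate is untouched, and averaged over random allocation the type I error stays near 5%. Figure 2, which shows the randomisation procedure, is not reproduced in the text available, so restricted allocation cannot be excluded. What randomisation does not do is correct the reported SE, or remove the movement of the estimate once an unequal split has occurred. Blocking would not prevent imbalance that arises from withdrawal.

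A second reply is that no drift is established, and that stands. The protocol calls acute illness a possible influence on appetite but describes no change across the four days. The background remark on taste fatigue concerns continued use of one supplement, whereas here the product changes at the period boundary and flavours are offered. It does not directly support a shift common to both products.

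A reader might infer that the planned test is biased, that its type I error is generally inflated, or that the crossover estimate itself becomes less precise. The documents support none of these. Bias needs both a shift and unequal analysed sequences. The raised error rate is conditional on a marked imbalance. At 25/25 only the reported uncertainty suffers.

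Finally, the study is exploratory and also relies on descriptive summaries. That limits the consequence, though the fix is cheap.

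**Conclusion.** The omission is real and the mechanism is algebraic, but its size depends on a shift, an SD and an imbalance that the documents do not give. Under the assumed SD of 30 points, a shift of 5 points or less with equal sequences costs about 1 point of power, and a shift of 15 points costs about 7. A 30/20 split moves the estimate by one fifth of the shift. This is a minor point: the comparison remains usable as planned, and the change is a cheap improvement. Period adjustment should not be read as dealing with carryover, or with selection if patients leave because a product did not suit them. It addresses neither.

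**What to change.** Amend Section 3 (Quantitative data analysis) and the matching sentence in Section 5.2.1, for patients with data in both periods:

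- **Where the paired t-test would be used:** compare within-patient period-1 minus period-2 differences between the two sequences with a two-sample t-test. Report half the difference in means (porridge-first minus liquid-first) with its 95% confidence interval. A model with product and period as fixed effects and patient effects is equivalent if fitted to the same complete pairs. A mixed model that also takes in single-period patients has a different analysis set.
- **Where Wilcoxon would be used, including the Likert items:** apply the Mann-Whitney test to the same period differences, and report half the Hodges-Lehmann shift with its confidence interval.
- **Reporting:** give the numbers analysed in each sequence.

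No new data are needed. Period and sequence follow from the dates and products on the data sheets and from the allocation. The cost is one degree of freedom. With no drift, power is unchanged at 25/25 (79%) and falls by about 2 points at 30/20.
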